10.14 Managing Data (Data Management and/or Sharing Plan) and/or Human Biological Specimens for

this Study:

Include in this section the plan for acquiring data (both electronic and hard copy), access during the study, data/specimen storage and length of time stored, shipment/transmission, and the plan for storage and final disposition at the conclusion of the study. Describe any data agreements in place for accessing data within and/or outside of your institution (e.g., Data Sharing Agreement, Data Use Agreement, Business Agreements, etc.)

A password protected master key will be managed by USU researchers and will be the only document that contains the participant name and participant identification number. The master key will be shared between performance sites and researchers via DoDSAFE. The performance site researchers will use this key to prevent errors when distributing the smoothies. If a hard copy of the master key is needed to assist distribution of the smoothies it will be stored in a locked draw in collaborator's office at the performance sites and shredded after all the results of the study have been obtained. Only aggregated results of this research will be presented at a conference and a manuscript will be developed.

Is this a data repository?

Yes No

10.15 Managing Data (Data Management and/or Sharing Plan) and/or Human Biological Specimens for Future Research:

If the study involves collecting, storing, or banking human specimens, data, or documents (either by the Investigator or through an established repository) for FUTURE research, address. How the specimens/data will be used, where and how data/specimens will be stored (including shipping procedures, storage plan, etc.), whether and how consent will be obtained, procedures that will fulfill subjects' request as stated in the consent, whether subjects may withdraw their data/specimens from storage, whether and how subjects may be recontacted for future research and given the option to decline, whether there will be genetic testing on the specimens, who will have access to the data/specimens, and the linkage, the length of time that data/specimens will be stored and conditions under which data/specimens will be destroyed.

N/A

Is this a data repository?

Yes No

11.0 Statistical/Data Analysis Plan

11.1 Statistical Considerations:

List the statistical methods to be used to address the primary and secondary objectives, specific aims, and/or research hypotheses. Explain how missing data and outliers will be handled in the analysis. The analysis plan should be consistent with the study objectives. Include any sub-group analyses (e.g., gender or age group). Specify statistical methods and variables for each analysis. Describe how confounding variables will be controlled in the data analysis

We plan to analyze results using multiple regression analysis whereby we will regress outcomes (O3I, ACFT scores) onto treatment-allocation, controlling for pre-treatment factors (e.g., pre-O3I, demographics). This is equivalent to a two-group ANCOVA. For most analyses, we aim to keep outcomes continuous. In sensitivity analyses, we will also dichotomize O3I (e.g., at 8%, which is the cutoff for healthy O3I), examine mixed generalized linear models, and examine the design-effect of each site (which may decrease power somewhat). Alternative model specifications or variable-transformations will be considered in cases where gross violations invalidate certain approaches.

11.2 Sample Size:

80-100 participants

11.3 Total number of subjects requested (including records and specimens):

100

11.4 If you are recruiting by study arm, please identify the arms of the study and how many subjects will be enrolled in each arm

N/A

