We hypothesize regular consumption (one smoothie per day, five days per week, for eight weeks) of omega-3 enhanced smoothies (1600 mg omega-3 per smoothie) will increase O3I to 8% compared to a control group. We also hypothesize improvements in performance markers related to strength, flexibility, aerobic capacity and power as assessed by the Army Combat Fitness Test (ACFT), rate of perceived exertion (RPE), and recovery (a visual analog scale (VAS) for pain) in the intervention group compared to control. We hypothesize the control group will not reach an O3I of 8% and measures of performance and recovery will be statistically lower than in the intervention group.

9.4 Study Design:

Describe study design in one to two sentences (e.g., prospective, use of existing records/data /specimens, observational, cross-sectional, interventional, randomized, placebo-controlled, cohort, etc.). Specify the phase – Phase I, II, III, or IV – for FDA-regulated investigational drug research

A double blind randomized-placebo control trial will be conducted in collaboration with the Army Holistic Health and Fitness (H2F) Program. Participants will be randomly selected from two H2F training sites: Ft. Campbell and Ft. Drum. In total, 100 participants will be randomly selected, 50 per site. Each site will have 25 participants assigned to the placebo group and 25 participants assigned to the omega-3 enhanced smoothie group. All interested soldiers will enter their name. Participants will be randomly selected until 100 participants consent. Participants will be excluded if they have a fish allergy or if they are unable to complete an Army Combat Fitness Test (ACFT) for any reason. Participants taking omega-3 supplements will not be excluded, but will be instructed to be consistent for the duration of the study.

9.5 Target Population:

Describe the population to whom the study findings will be generalized

Soldiers

9.6 Benefit to the DoD:

State how this study will impact or be of benefit to the Department of Defense

Previous research already indicates omega-3 status is low in military personal. Increasing omega-3 fatty acid intake will not only help maintain a healthy force by minimizing chronic disease risks, if we determine omega-3 fatty acids improve performance or recovery, then guidelines can be developed and soldiers can be educated and the demand for these types of foods will lead the way in improving the military nutrition environment.

10.0

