11.5 Please provide a justification for your sample size

Power calculations, performed using the pwr2ppl package in r (<https://www.routledge.com/Applied-Power-Analysis-for-the-Behavioral-Sciences-2nd-Edition/Aberson/p/book/9781138044593>), were executed based on the expected associations between treatment allocation (i.e., treatment vs control) and the outcome variables (post-O3I, ACFT scores), controlling for baseline statuses (e.g., pre-O3I). We also assumed there would 20% be missing data or attrition, and that baseline statuses would not be associated with treatment allocation. Alpha was set alpha at 0.05 and power at 0.8. Under these conditions, with an analytic sample size of 80 subjects, and assuming a correlation between pre- and post-O3I (or pre- and post-ACFT score) of 0.6, the study will be adequately powered to detect an association of $r = 0.25$ between treatment allocation and the outcome. This converts into a cohen's d (or standardized-unit difference) of 0.55. This is generally considered a moderate-to-strong effect size. Based on previous research examining distribution and change in O3-I in similar samples, this would likely be equivalent to a treatment-effect of 0.6%-unit increase in O3-I. If there is a weaker association between pre- and post-O3I (or other outcomes), then the minimal detectable effect size would increase (e.g., if the pre/post association is 0.4, then the minimal detectable effect would be a Cohen's d of 0.6); if there is a stronger association between pre- and post-O3I, then the minimal detectable effect size would decrease (e.g., if the pre/post association is 0.8, then the minimal detectable effect would be a Cohen's d of 0.4).

11.6 Data Analysis Plan: Complete description: Background, Objectives, Design, Step by Step how the project is going to be done, Data analysis plan:

In addition to the analyses indicated in 11.1, additional measures will be undertaken to ensure that data are of high-quality over the course of the study, including double data entry where relevant, periodic inspection of data as it is collected, and periodic preliminary analyses. Statistical packages to be used will primarily include Microsoft Office Excel and IBM SPSS.

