12.4 Special categories, check all that apply

- Minors /Children
- Students
- Employees - Civilian
- Employees - Contractor
- Resident/trainee
- Cadets /Midshipmen
- Active Duty Military Personnel
- Wounded Warriors
- Economically Disadvantaged Persons
- Educationally Disadvantaged Persons
- Physically Challenged (Physical challenges include visual and/or auditory impairment)
- Persons with Impaired Decisional Capacity
- Prisoners
- Pregnant Women, Fetuses, and Neonates
- Non-English Speakers
- International Research involving Foreign Nationals - Headquarters Review is necessary

You must also consider the requirements of DoDI 3216.02, Enclosure 3, paragraph 7.e.

12.5 Inclusion Criteria:

Order Number	Criteria
1	Current soldier at Ft. Drum or Ft. Campbell.
2	Able and willing to complete two Army Combat Fitness Test (ACFT) (Week 1 and week 8)
3	Willing to obtain two finger pricks for the Omega-3 Index (week 1 and week 8)

12.6 Exclusion Criteria:

Order Number	Criteria
1	Allergic to fish

13.0

Recruitment and Consent

13.1 Please describe the recruitment process, including how subjects will be identified and selected for the study.

Recruiting

Recruitment will be done by briefing select companies where command has approved the soldiers to participate (See recruitment brief). Volunteers who are interested and meet the eligibility criteria will provide their name and email address. Once recruitment has ended participants will be randomly selected to participate and notified by email. Participants selected will review the eICD with researchers. Once all 100 participants are selected and have signed the electronic informed consent (eICD) they will be allocated to either the intervention (smoothie enhanced with omega-3) or placebo (smoothie with no omega3) group.

13.2 Compensation for Participation:

N/A

13.3 Please describe the pre-screening process. If no pre-screening, enter Not Applicable in the text editor

N/A

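### Site is left out of the named ANCOVA terms and is expected to cost power, although arms are balanced 25:25 within each site and adjusting for site would keep or raise power

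*Combined protocol and SAP*

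**What the plan says.** Section 9.4 sets the allocation by site: "Each site will have 25 participants assigned to the placebo group and 25 participants assigned to the omega-3 enhanced smoothie group". Section 13.1 allocates individuals after consent: "they will be allocated to either the intervention (smoothie enhanced with omega-3) or placebo (smoothie with no omega3) group". It does not mention stratification, so the within-site balance rests on section 9.4.

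Section 11.1 regresses each outcome on treatment allocation, "controlling for pre-treatment factors (e.g., pre-O3I, demographics"). The covariate list is open, so site is unnamed rather than excluded. Site appears only among the sensitivity analyses, where the plan will "examine the design-effect of each site (which may decrease power somewhat").

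The power calculation in section 11.5 has no site term. It works "with an analytic sample size of 80 subjects", "assuming a correlation between pre- and post-O3I (or pre- and post-ACFT score) of 0.6". "Alpha was set alpha at 0.05 and power at 0.8".

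**The concern.** Fixing the arms within site makes site a stratum of the design. A difference between sites then cancels from the treatment contrast, because it raises or lowers both arms equally. If the model has no site term, that difference does not disappear. It goes into the residual, so the reported standard error exceeds the true sampling error, the confidence interval is too wide and the test is conservative.

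Site differences are plausible here, though not quantified. The fitness tests are run by Army staff for whole companies, and smoothies are handed out locally (sections 10.1 and 10.2).

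The plan expects the opposite of what a balanced within-site comparison gives. That remark offers a reason to keep site out of the main model, and the open covariate list leaves the choice to be made after the data are seen. Planned power is only 0.8 with 80 analysed, so an avoidable loss is worth removing.

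**Working it through.** **Inputs.** From section 11.5: 80 analysed (100 less 20%), alpha 0.05, power 0.8, pre/post correlation 0.6, detectable r = 0.25. From section 9.4: two sites, 25:25 in each, hence 20:20 after even attrition. Assumed: a two-sided test (sidedness is not stated) and the share of residual variance due to site (not given; 0 to 20% shown).

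**The plan's own figure.** For one coefficient in a regression that also has the baseline value, f² = r²/(1 − r² − 0.6²) = 0.0625/0.5775 = 0.108. With 77 df and noncentrality 77f², power is 0.813, so r = 0.25 is consistent with the stated 0.8. The stated d = 0.55 does not follow from it: 2r/√(1 − r²) = 0.516. That is a separate matter. The smallest d with 80% power under this ANCOVA is about 0.508, and the simulations below use 0.507.

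**Which design effect applies.** With m = 40 analysed per site and site share ρ:
- Whole sites randomised: variance factor 1 + (m − 1)ρ, which at ρ = 0.05 is 1 + 39 × 0.05 = 2.95.
- Arms balanced within site, as here, with site in the model: variance factor 1 − ρ, which at ρ = 0.05 is 0.95.

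Only the first reduces power, and it is not this design.

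**Standard error without site.** It is too large by roughly 1/√(1 − ρ): 1.005, 1.010, 1.026, 1.054 and 1.118 at ρ = 1%, 2%, 5%, 10% and 20%. Simulation gives 0.5%, 1.0%, 2.7%, 5.5% and 12%.

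**Type I error and power.** 100,000 simulated trials per scenario, 20 per site-by-arm cell, outcome = 0.6 × baseline + site shift + effect + error, fitted by least squares with and without a fixed site term. The residual variance is 1 − 0.6² = 0.64. The 0.6 correlation can be read in two ways:
- *Pooled over sites:* total residual variance stays at 0.64. Shares of 5%, 10% and 20% correspond to site shifts of 2√(0.64ρ) = 0.36, 0.51 and 0.72 SD.
- *Within site:* within-site variance is 0.64 and site variance is added on top. The shifts are 0.37, 0.53 and 0.80 SD.

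| Site share | Type I error without site | Power without / with site, pooled | Power without / with site, within-site |
|---|---|---|---|
| 0% | 0.050 | 0.793 / 0.793 | 0.793 / 0.793 |
| 5% | 0.045 | 0.799 / 0.814 | 0.780 / 0.794 |
| 10% | 0.039 | 0.807 / 0.835 | 0.761 / 0.793 |
| 20% | 0.029 | 0.818 / 0.875 | 0.719 / 0.793 |

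Type I error with site is 0.050–0.051. At shares of 1–2% the power difference is under 1 point. Monte Carlo error is about 0.0007 for type I error and 0.0013 for power.

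**Unequal cells.** With 80 drawn at random from the four groups of 25 (20,000 trials, pooled reading), power without / with site is 0.792/0.792, 0.799/0.812, 0.803/0.834 and 0.812/0.873 at shares of 0, 5%, 10% and 20%. Type I error without site is 0.052, 0.047, 0.043 and 0.032. With opposite imbalance in the two sites (22/18 and 18/22), adjusting costs about 0.5 point if site explains nothing and gains 1.5 and 3.5 points at 5% and 10%.

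**The case against.** The strongest reply is that the phrase in section 11.1 is ambiguous and stands beside a plan to examine mixed models. If it means an effect estimated separately at each site (20 per arm), power is about 50% at d = 0.507 and 56% at d = 0.55, and the caution is right. If it means a treatment effect that varies randomly between sites, with the two sites as the unit of inference (1 df), power at d = 0.55 is about 15–20%, and the caution is right again. But section 11.1 specifies neither, and design effect is not the usual term for site-specific treatment effects. The conclusion is limited to a fixed site main effect. If something else was intended, the plan should say so.

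The points about size stand as limits:
- Shares of 10% and 20% need site shifts of 0.51 and 0.72 SD to remain after baseline adjustment, as large as or larger than the treatment effect simulated, and the baseline value will absorb part of any stable site difference.
- At the plan's own d = 0.55 (pooled reading), power without / with site is 0.865/0.876, 0.871/0.892 and 0.885/0.924, so the gain is about 1, 2 and 4 points.
- On the pooled reading, which suits a calculation with a single correlation and no site term, planned power is kept and only a gain is forgone. The shortfall below 0.8 needs the within-site reading.
- With random dropout the test is somewhat less conservative than with equal cells.

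None of this gives a reason to leave site out.

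**Conclusion.** The concern holds. For two sites with arms balanced inside each, the stated expectation about power is reversed: a fixed site term has no material cost and helps whenever site predicts the outcome after baseline adjustment. Leaving it out makes the analysis conservative, not biased. The loss is modest and depends on a site variance that the documents do not give: negligible at 1–2% of residual variance, and about 1.5, 3 and 6 to 7 points of power at 5%, 10% and 20% for an effect near the 80% power threshold. The result assumes a two-sided 0.05 test, a site main effect and no random treatment-by-site effect. The change should be made because it is almost free and settles a modelling choice before the data are seen.

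**What to change.** In section 11.1:
- Name site as a fixed effect in every main ANCOVA: post-intervention value on allocation, baseline value and site.
- Delete the remark that site may decrease power.
- Replace the design-effect sensitivity analysis with a site-by-treatment interaction, reported as an estimate with a confidence interval and labelled descriptive. It is the difference between two site-specific effects, each with variance 4σ²/40, so its variance is 8σ²/40 = 16σ²/80, against 4σ²/80 for the main effect. Its standard error is therefore about twice as large.

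It would also help to state in section 13.1 that allocation is stratified by site, as section 9.4 implies.

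The cost is one covariate (1 df) and a sentence or two, with no change to sample size or data collection.

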11.5 Please provide a justification for your sample size

Power calculations, performed using the pwr2ppl package in r (<https://www.routledge.com/Applied-Power-Analysis-for-the-Behavioral-Sciences-2nd-Edition/Aberson/p/book/9781138044593>), were executed based on the expected associations between treatment allocation (i.e., treatment vs control) and the outcome variables (post-O3I, ACFT scores), controlling for baseline statuses (e.g., pre-O3I). We also assumed there would 20% be missing data or attrition, and that baseline statuses would not be associated with treatment allocation. Alpha was set alpha at 0.05 and power at 0.8. Under these conditions, with an analytic sample size of 80 subjects, and assuming a correlation between pre- and post-O3I (or pre- and post-ACFT score) of 0.6, the study will be adequately powered to detect an association of $r = 0.25$ between treatment allocation and the outcome. This converts into a cohen's d (or standardized-unit difference) of 0.55. This is generally considered a moderate-to-strong effect size. Based on previous research examining distribution and change in O3-I in similar samples, this would likely be equivalent to a treatment-effect of 0.6%-unit increase in O3-I. If there is a weaker association between pre- and post-O3I (or other outcomes), then the minimal detectable effect size would increase (e.g., if the pre/post association is 0.4, then the minimal detectable effect would be a Cohen's d of 0.6); if there is a stronger association between pre- and post-O3I, then the minimal detectable effect size would decrease (e.g., if the pre/post association is 0.8, then the minimal detectable effect would be a Cohen's d of 0.4).

11.6 Data Analysis Plan: Complete description: Background, Objectives, Design, Step by Step how the project is going to be done, Data analysis plan:

In addition to the analyses indicated in 11.1, additional measures will be undertaken to ensure that data are of high-quality over the course of the study, including double data entry where relevant, periodic inspection of data as it is collected, and periodic preliminary analyses. Statistical packages to be used will primarily include Microsoft Office Excel and IBM SPSS.

12.0 Participant Information**12.1 Subject Population:**

Holistic Health and Fitness Soldiers

12.2 Age Range:

Check all the boxes that apply. if the age range of potential subjects (specimens, records) does not match the range(s) selected, please specify in the text box.

- 0-17
- 18-24
- 25-34

- 35-44
- 45-54
- 55-64
- 65-74
- 75+

12.3 Gender:

- Male
- Female
- Other

12.4 Special categories, check all that apply

- Minors /Children
- Students
- Employees - Civilian
- Employees - Contractor
- Resident/trainee
- Cadets /Midshipmen
- Active Duty Military Personnel
- Wounded Warriors
- Economically Disadvantaged Persons
- Educationally Disadvantaged Persons
- Physically Challenged (Physical challenges include visual and/or auditory impairment)
- Persons with Impaired Decisional Capacity
- Prisoners
- Pregnant Women, Fetuses, and Neonates
- Non-English Speakers
- International Research involving Foreign Nationals - Headquarters Review is necessary

You must also consider the requirements of DoDI 3216.02, Enclosure 3, paragraph 7.e.

12.5 Inclusion Criteria:

Order Number	Criteria
1	Current soldier at Ft. Drum or Ft. Campbell.
2	Able and willing to complete two Army Combat Fitness Test (ACFT) (Week 1 and week 8)
3	Willing to obtain two finger pricks for the Omega-3 Index (week 1 and week 8)

12.6 Exclusion Criteria:

Order Number	Criteria
1	Allergic to fish

13.0

Recruitment and Consent

13.1 Please describe the recruitment process, including how subjects will be identified and selected for the study.

Recruiting

Recruitment will be done by briefing select companies where command has approved the soldiers to participate (See recruitment brief). Volunteers who are interested and meet the eligibility criteria will provide their name and email address. Once recruitment has ended participants will be randomly selected to participate and notified by email. Participants selected will review the eICD with researchers. Once all 100 participants are selected and have signed the electronic informed consent (eICD) they will be allocated to either the intervention (smoothie enhanced with omega-3) or placebo (smoothie with no omega3) group.

13.2 Compensation for Participation:

N/A

13.3 Please describe the pre-screening process. If no pre-screening, enter Not Applicable in the text editor

N/A

13.4 Consent Process: Revised Common Rule, Section 219.116: General requirements for informed consent, whether written or oral, are set forth in this paragraph and apply to consent obtained in accordance with the requirements set forth in paragraphs (b) through (d) of this section. Broad consent may be obtained in lieu of informed consent obtained in accordance with paragraphs (b) and (c) of this section only with respect to the storage, maintenance, and secondary research uses of identifiable private information and identifiable biospecimens.

Are you requesting a waiver or alteration of informed consent?

Yes No

Please explain the consent process:

Consenting

Participants that are interested and eligible will review the ICD with a member of the research team. The participant will be encouraged to ask any questions he/she has, both in writing as part of the ICD and verbally by the person conducting the consent process. Once all questions have been answered to the volunteer's satisfaction, he/she will be given a USU-approved tablet to do an electronic (e) consent using the USU REDCap capabilities. They will provide an e-signature and a copy of the consent form will be emailed to them with their permission. Once the consent document is signed, they will be enrolled in the study. As an alternative, paper ICD forms will be available in case there are technical issues.

13.5 DoDI 3216.02 requires an ombudsman to be present during recruitment briefings when research involves greater than minimal risk and recruitment of Service members occurs in a group setting. If applicable, you may nominate an individual to serve as the ombudsman.

N/A

Propose ombudsman

13.6 Withdrawal from Study Participation:

Explain the process for withdrawal and specify whether or not the subjects will be given the opportunity to withdraw their data their data/specimens in the event they wish to withdraw from the study

Information about processes for withdrawing from the study will be provided to participants at the time of consent. A participant may decide to withdraw from the study at any time. Refusal to participate will involve no penalty or loss of benefits to which the subject is otherwise entitled and the subject may discontinue participation at any time without penalty or loss of benefits to which the subject is otherwise entitled. If a participant withdraws, any previously collected data will be retained unless they provide written request for removal of your data in the withdrawal letter.

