Study Procedures, Data Management, and Privacy

10.1 Study Procedures:

Describe step-by-step how the study will be conducted from beginning to end

This is an 8-week protocol with baseline and post-intervention data collections including: demographics, digitized questionnaires (nutrition, physical activity and sleep), O3I (collected by finger prick) and ACFT scores. We will assess changes in O3I status, performance on, and recovery from the ACFT at two H2F training sites (Ft. Campbell and Ft. Drum), after providing omega-3 enhanced or placebo smoothies. All smoothies will be pre-made, iso-caloric and provided in similar ready to drink containers. Researchers and participants will be blinded, one staff member will not be blinded and maintain the key identifying which participants receive the placebo vs intervention. A smoothie log based on participant ID will be coded (i.e., A or B) to assist in distribution of the smoothies. Each smoothie will have a lot number that ends in A or B.

Baseline visit: To account for potential confounding factors, dietary intake assessed using the Health Eating Score (HES), daily physical activity using the Physical Activity Questionnaire (PAQ), and sleep using the Pittsburg Sleep Quality Index (PSQI) sleep questionnaire will be collected using REDCap. O3I will be collected by finger prick. A baseline ACFT will be conducted by trained Army staff (not researchers). The ACFT scores will be reported to the researchers by the participants. Participants will log into REDCap to report their ACFT score and report the Rate of Perceived Exertion (RPE), a score of 6-20 and the pain score, ranging from 0-10. This will be recorded one hour and 24 hour post ACFT.

Intervention: To ensure compliance, participants will be provided an omega-3 smoothie or placebo daily (Monday-Friday) by brigade dietitians or assigned staff immediately following training.

Post-Intervention data collection: After eight weeks of intervention O3I, questionnaires and ACFT scores will be collected again with participants reporting their RPE and pain scores following the same format as the baseline visit.

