14.0 Risks and Benefits

14.1 Risks of Harm:

Identify all research-related risks of harm to which the subject will be exposed for each research procedure or intervention as a result of participation in this study. Consider the risks of breach of confidentiality, psychological, legal, social, and economic risks as well as physical risks. Do not describe risks from standard care procedures; only describe risks from procedures done for research purposes

All of the research procedures described are associated with minimal risk, but there are still expected risks and potential reasons to stop data collection. For example, there is potential risk associated with the finger prick. Participants may experience some discomfort, and some bruising and/or transient pain at the site of the finger prick. In addition, there are slight risks of infection. There is also a risk of an allergic reaction, if a participant has an unknown food allergy.

14.2 Measures to Minimize Risks of Harm (Precautions, safeguards):

For each research procedure or intervention, describe all measures to minimize and/or eliminate risk of harms to subjects and study personnel

To minimize risk participants will be given specific instructions to clean the finger with an alcohol pad prior to the O3I prick. Participants will be informed they can put ice on their finger if it is sore, or to minimize potential soreness. During the consenting process participants will be informed of common signs of infection, including redness and swelling, and instructed to go the medical clinic if they have any symptoms 24 hours after the finger prick.

To minimize harm from an allergic reaction researchers will monitor participants as they drink the beverage and watch for any signs of intolerance. Medical help will be called if there are signs or symptoms of an allergic response.

14.3 Confidentiality Protections (for research records, data and/or specimens):

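### Fish is the only allergy exclusion, although both arms drink a smoothie with other ingredients; the eligibility and risk sections need a one-line repair

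*Combined protocol and SAP*

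**What the plan says.** **Exclusions.** Section 12.6 has a single entry: "Allergic to fish". Section 9.4 agrees: "Participants will be excluded if they have a fish allergy". Its only other ground is inability to complete the Army Combat Fitness Test (ACFT).

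**Inclusion and screening.** The three inclusion criteria in 12.5 concern the post at which the soldier serves, the two fitness tests and the two finger pricks. None concerns food allergy or fitness to consume the product. Section 13.3, on pre-screening, is answered N/A.

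**Product.** Section 10.1 says of both arms: "All smoothies will be pre-made, iso-caloric and provided in similar ready to drink containers". Section 13.1 describes the control product as "placebo (smoothie with no omega3) group". The hypothesis in 9.3 gives the schedule as "one smoothie per day, five days per week, for eight weeks", and 10.1 applies Monday-to-Friday provision to both products.

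**Risk.** Section 14.1 states: "There is also a risk of an allergic reaction, if a participant has an unknown food allergy". Section 14.2 responds with observation while the participant drinks and a call for medical help if signs of a reaction appear. Section 16.1 deals with dislike of the drink and poor tolerance after hard exercise, but not with a known allergy.

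**The concern.** The plan treats food allergy both as a ground for exclusion and as a research risk, but the exclusion covers only the allergen linked to the omega-3 source. A smoothie without omega-3 must be made of something else, and the active smoothie presumably shares much of that base. No criterion addresses a known allergy to it.

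The wording of 14.1 makes the gap harder to see. Confining the residual risk to allergies nobody knew about gives a full account only if the relevant known allergies have been removed beforehand. The criteria do that for fish alone.

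At stake is a preventable exposure of a soldier who could have been identified by one question, and a risk statement that does not match the eligibility rule. Estimation and testing are not affected.

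**Working it through.** The plan gives no figure on this point, so there is none to reproduce. The check is whether any written step would stop a volunteer with a known non-fish food allergy, taken in the order in which volunteers meet the steps.

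1. **Recruitment brief (13.1).** Interested volunteers who meet the criteria give a name and email address. The criteria applied here are those of 12.5 and 12.6. Such a volunteer passes all three inclusion criteria and is not caught by the fish exclusion.
2. **Pre-screening (13.3).** N/A, so no step here.
3. **Random selection (9.4, 13.1).** Drawn from the names given, with no further eligibility test described.
4. **Consent (13.1, 13.4).** The volunteer reviews the consent document with a team member and may ask questions. This is an opportunity to raise an allergy, but no rule makes it disqualifying.
5. **Allocation (9.4, 13.1).** At each of two sites, 25 are assigned to placebo and 25 to omega-3: 2 × 25 = 50 per arm and 2 × 50 = 100 in all. The volunteer can fall in either arm.
6. **Exposure (9.3, 10.1).** 5 smoothies per week × 8 weeks = 40 servings offered. This is a ceiling on what is offered, not an estimate of what such a person would drink.
7. **Observation (14.2).** This begins when the participant drinks. It can limit the harm of a reaction but cannot prevent the exposure.

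No written step excludes this volunteer.

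Setting the sections side by side:

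| Type of allergy | Excluded by 9.4 / 12.6? | Described as a risk in 14.1? |
|---|---|---|
| Known, to fish | Yes | Not needed, since excluded |
| Unknown, to any food | Cannot be | Yes |
| Known, to another ingredient | No | No |

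The third row is the gap: neither section covers it.

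One step is inference. The documents do not list ingredients. That both products contain foodstuff other than the omega-3 source follows from a placebo smoothie without omega-3 that is matched for calories. Which ingredients these are, and whether any is a common allergen, cannot be determined.

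**The case against.** The strongest reply is that the hazard itself is not shown. With no ingredient list, no allergen can be named. The recruitment brief cited in 13.1 and the consent pages are where ingredients would be disclosed, and neither was available. A soldier who knows of a food allergy would have to attend a briefing about a smoothie study, review consent individually, sign, and never mention it. Staff also watch participants drink. Finally, 14.1 says that a risk exists when an allergy is unknown; it does not claim that every known allergy was screened out, so the wording is incomplete rather than contradictory.

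Most of this stands as a limit on size. It does not close the gap: disclosure would inform volunteers without changing the written criterion, and observation does not screen.

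Three stronger readings are tempting and not supported:

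- **That enrolling at least one such soldier is likely.** A probability could be attached by assuming a prevalence, but the documents supply none. Prevalence of allergy to unspecified ingredients cannot be bounded away from zero, and such a calculation would ignore self-exclusion by people who know their allergy.
- **That such a participant would be lost at week 8.** Nothing in the plan ends data collection when the smoothie is stopped. The ACFT is run for the whole company (10.2), the Omega-3 Index needs only a finger prick, and 13.6 concerns withdrawal from the study. A few losses would in any case fall within the 20% allowance in 11.5 (100 × 0.80 = 80 analysed).
- **That the risk statement misled the IRB.** This cannot be judged without the brief and the consent form.

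**Conclusion.** The point holds as a minor participant-safety and eligibility gap. The criteria admit a volunteer with a known allergy to a smoothie ingredient other than fish, and 14.1 does not describe that risk. Confidence is high on the wording of the criteria and much lower on the practical hazard, which depends on a recipe the documents do not give.

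The number affected is probably small because of self-exclusion at consent, and no figure should be attached to it. The sample size, the power calculation and the ANCOVA are untouched. The conclusion assumes only that both smoothies contain foodstuff other than the omega-3 source.

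**What to change.** 1. In 12.6, and in the matching sentence of 9.4, widen the exclusion to a known allergy to fish or to any other ingredient of either smoothie. This wording works whatever the recipe is.
2. Unless the recruitment brief already does so, give every volunteer one combined ingredient list covering both smoothies before names are taken. A single list, the same for everyone, does not reveal the arm.
3. Reconcile 14.1 with the criteria. Once the exclusion is widened, confining the residual risk to unknown allergies is accurate.

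The cost is one line in each of two sections, a check of 14.1, and at most an ingredient list in the brief. The small downside is that a few volunteers become ineligible before selection. Section 9.4 draws volunteers until 100 have consented, so they are replaced from the pool before allocation, and the planned numbers per arm stay the same.
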